13.3 Guidelines for Lead Institution and Other Site Institutions

Patients should be registered in the electronic database, ONCORE as soon as the patient has signed the informed consent. Following registration, the patient's enrollment status in the electronic database will be listed as pending. Prior to randomization the eligibility criteria must be reviewed and confirmed by the site PI and the coordinating center. Eligibility data will then be entered in the electronic database and the subject will be randomized. Study treatment may begin only after eligibility has been confirmed by both a site PI and the coordinating center. Once eligibility has been reviewed, it is recommended that treatment begin within a timely manner.

13.3 Eligibility exceptions

Any requests for protocol exceptions must be approved in writing by [name] at the Lester & Sue Smith Breast Center. Request for protocol exceptions must be made via email or fax to the lead study coordinator. Both [name] and the local PI should be copied on all requests and associated correspondence. Once a determination has been made, the site study coordinator and local PI will be notified in writing. In the event that an eligibility exception is granted by the

coordinating center, the local site must submit the exception to their local IRB in accordance with institutional standard operating procedures.

13.4 Primary Endpoint

Descriptive and summary statistics will be computed for all demographic and clinical data in each treatment group. The HAQ-II will be used to assess joint pain symptoms; a higher score indicates more severe joint pain. Scores will be evaluated for the development of AIA between baseline and Week 12, as well as between baseline and Week 52, though development of AIA at 12 weeks will be the primary endpoint. The scores will be dichotomized as “development of AIA” (as defined above, in Section 12.2) or “no development of AIA.” Group differences in AIA rate will be assessed using the Chi-square test. Development of AIA at week 12 will be used to test the primary objective. The week 52 data will be measured and reported as well. As exploratory analyses, development of AIA will be assessed using logistic regression, adjusting for potential confounders such as age at diagnosis, race/ethnicity, BMI, receipt of chemotherapy, taxane use, and use of hormone replacement therapy. All statistical tests are one-sided with $\alpha = 0.10$ as the level of significance.

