6.1 Screening and Baseline assessments

A signed, written informed consent must be obtained before any study-specific assessments are initiated. Results from assessments performed prior to written consent as part of a patient's routine diagnostic workup may be used for screening purposes. The following assessments will be obtained at screening, within 28 days prior to beginning study medication:

- Subject demographic information, to include age, ethnicity, and race
- Medical history, including past and current conditions, and past surgical history
- Whether patient has used Hormone Replacement Therapy (HRT), for how many years, and how long ago she stopped.
- Use of chemotherapy, including taxanes or not including taxanes
- Measurement of body weight, height, and Body Mass Index
- Completion of Health Assessment Questionnaire (HAQ-II)

- Grip strength measurement
- Laboratory assessments to include:
 - Calcium level
 - Albumin level
 - Vitamin D level -- serum 25(OH)D
 - FSH, LH, and estradiol levels must be obtained if required as detailed above in 4.1.4 to determine menopausal status. Menopausal status should be interpreted by the treating physician and approved by study chair based on the cutoff values provided by the reporting laboratory.
- Review of all medications taken within 28 days of planned treatment start date
- Study coordinator will educate the patient about the importance of compliance with Aromatase Inhibitor therapy.
- If a Bone Mineral density test has not been completed within 3 months of starting AI therapy, a Bone Mineral Density test must be ordered as a screening assessment, and the test must be completed within 28 days of starting Aromatase Inhibitor therapy

If the above studies are within acceptable parameters as defined by the eligibility criteria, the patient will be randomized to begin either high dose Vitamin D or standard dose Vitamin D, as described in [Section 7](#).

6.2 Follow-up at Week 4

The following assessments should be performed at 4 weeks (28 days) from the start of study medication. To allow for weekends, holidays, etc., study procedures may be completed within a window of +/- 5 business days.

- Laboratory assessments to include a calcium level, 25-hydroxyvitamin D level, and albumin.

6.3 Follow-up at Week 12

- Measurement of body weight and BMI
- Laboratory assessments to include a calcium level, 25-hydroxyvitamin D level, and albumin.
- Patient is to complete the Health Assessment Questionnaire (HAQ-II)

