6.8 On Study Assessments and Procedures

6.8.1 Health Assessment Questionnaire

Each subject will be asked to complete the Health Assessment Questionnaire (HAQ-II) at baseline, 12 weeks, and 52 weeks. The questionnaire will be completed in the office, during the clinic visit, and it will be administered by the study coordinator. Generally, the questionnaire can be completed in less than 5 minutes by most patients. The questionnaire will be available in English, Spanish, and Vietnamese.

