12. MEASUREMENT OF EFFECT

The primary assessments for this study will be the average score on the Health Assessment Questionnaire (HAQ-II), as well as the score from the visual analog scale.

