12.2 Measurement of Aromatase Inhibitor-Induced Arthralgia

Many trials which specifically examine AIA or other joint pathologies use a widely validated clinical tool termed the Health Assessment Questionnaire (HAQ-II). It is commonly used in rheumatology literature, and has been substantiated across many trials. This is a simple survey, which is a proven, reliable, and accurate indicator of joint pains and consequent disabilities (14) (15). An abbreviated version of the HAQ-II, which takes about 5 minutes to complete, will be used in the study (see Appendix A).

This questionnaire asks 20 questions in 8 categories of functioning: dressing, rising, eating, walking, hygiene, reach, grip, and usual activities. For each question, the patient is scored on a scale of 0-3, depending on how much difficulty they have performing the task. A score of 0 correlates with no difficulty at all, and a score of 3 denotes that the patient is unable to do the task. The highest numerical score from each category is used, and the average of these 8 numbers is the composite score on the HAQ-II. Scores of 0-1 are considered to represent mild to moderate difficulty, 1-2 represents moderate to severe disability, and 2-3 represents severe to very severe disability. Average score in a population based study is 0.49, whereas patients with osteoarthritis and rheumatoid arthritis have average scores of 0.8 and 1.2, respectively. Most investigators agree that “minimal clinical important difference” is 0.2 (42). Thus, the study uses this as a cut-off point.

The visual analog scale is the other major component of the HAQ-II. In this, the patient is asked to mark, with a vertical line, where their pain lies on a horizontal line which is 15 cm long, with the far left side of the line representing no pain at all, and the far right side representing unbearable pain. To obtain the individual’s score, the distance between the far left side of the line and the patient’s mark is multiplied by 0.2. This converts the number of centimeters into the appropriate score and will yield a value from 0 to 3.

For the purposes of this study, AIA will be defined as any of the following criteria: 1) increase in HAQ-II score from baseline by 0.2 or greater; or 2) increase in visual analog pain score by 0.3 or greater. The HAQ-II questionnaire and its visual analog pain score are used in the definition of

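### The exploratory adjusted model for week-12 AIA names six covariates but neither baseline HAQ-II nor baseline pain, the two scores from which AIA is defined

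*Combined protocol and SAP*

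**What the plan says.** Section 12.2 counts a woman as having AIA if she has an "increase in HAQ-II score from baseline by 0.2 or greater; or 2) increase in visual analog pain score by 0.3 or greater". The pain scale is on the same form: "The visual analog scale is the other major component of the HAQ-II". Section 12 says that the primary assessments "will be the average score on the Health Assessment Questionnaire (HAQ-II), as well as the score from the visual analog scale". Section 6.8.1 fixes the timing: "Each subject will be asked to complete the Health Assessment Questionnaire (HAQ-II) at baseline, 12 weeks, and 52 weeks". Both starting values therefore exist for the analysis.

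For the primary comparison, section 13.4 states: "Group differences in AIA rate will be assessed using the Chi-square test". The same section then adds a second tier: "As exploratory analyses, development of AIA will be assessed using logistic regression". Six covariates are given for that model by way of example: "adjusting for potential confounders such as age at diagnosis, race/ethnicity, BMI, receipt of chemotherapy, taxane use, and use of hormone replacement therapy". The wording makes the list illustrative rather than closed.

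Section 13.5 has one other logistic model for AIA that contains treatment. Its target is baseline vitamin D, and it names no further covariates. The section 13.4 model is thus the only one aimed at an adjusted comparison of the arms.

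**The concern.** When an outcome is a rise past a threshold, it depends on where the patient starts. On 0-3 scales, a woman with baseline pain above 2.7 cannot rise by 0.3, and one with HAQ-II above 2.8 cannot rise by 0.2. More commonly, regression to the mean makes a rise less likely for a woman who starts high. If the high-dose arm happens to start higher, its AIA rate falls without any treatment effect. If it starts lower, a real effect is partly hidden.

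The named covariates are reasonable, and section 1.2 gives some support for BMI, hormone replacement therapy and chemotherapy. None of them defines the endpoint. The baseline scores could be added later under the open list, but by then the by-arm summaries would have shown any imbalance and the choice would be post hoc. At stake is how far a supportive result can be trusted when the arms differ at baseline. The primary test itself is not in question.

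**Working it through.** **1. The plan's sample size reproduces.** Inputs from section 13.2: 33% against 19%, one-sided alpha 0.10, power 80%. The average rate is 0.26.

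n = [1.2816 × √(2 × 0.26 × 0.74) + 0.8416 × √(0.33 × 0.67 + 0.19 × 0.81)]² / 0.14² = 87.6, so 88 per group.

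Then 88/0.95 = 92.6, so 93. Power at 93 per arm is 81.8%. The unadjusted design is sound on its own terms.

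**2. Link between baseline and change.** If baseline and week-12 scores have equal SDs and correlation r, the correlation of baseline with change is −√((1 − r)/2), before clipping and thresholding. This gives −0.39 at r = 0.7, −0.27 at 0.85 and −0.22 at 0.9. The link is real but weakens as r rises.

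**3. How large chance imbalance is.** For one score the SD of the arm difference is √(2/93) = 0.147 SD units. For the mean of the two scores, with an assumed HAQ-pain correlation of 0.5, it is 0.147 × √0.75 = 0.127. The top 10% of trials therefore starts at 1.2816 × 0.127 = 0.16 SD. A difference above 0.30 SD occurs in 0.9% of trials.

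**4. Simulation, 93 per arm, one-sided 10%.** Assumptions not in the documents: HAQ SD 0.4, scored in eighths; pain mean 0.5 and SD 0.5; HAQ-pain correlation 0.5; week-12 means set so that AIA is 33%. Baseline HAQ mean is 0.35 or 0.49; the latter is the population average in section 12.2. There were 50,000 null trials per setting, and the Monte Carlo SE within a decile is 0.4-0.8 points.

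| Assumed r | AIA rate with no mean change | Chi-square error, high-dose arm starts highest (10% of trials) | Chi-square error, high-dose arm starts lowest (10% of trials) |
|---|---|---|---|
| 0.7 | 32-34% | 15.1-16.0% | 5.1-5.3% |
| 0.85 | 22-24% | 12.3-12.7% | 6.4-7.3% |
| 0.9 | 16-18% | 10.7-12.4% | 8.1-8.8% |

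Treatment plus both baseline scores gave 9.7-11.0% and 9.5-10.7% in those two deciles.

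A repeat with 6,000 trials per setting (HAQ mean 0.49) had 600 trials per decile, so an SE near √(0.12 × 0.88/600) = 1.3 points. In the highest decile it gave 17.3%, 11.8% and 13.3% for the chi-square, 9.5-12.8% for the three-term model and 9.5-12.2% for a ten-term model with the six listed covariates added. With SDs of 0.3 and 0.4 the chi-square figures were 16.7%, 14.0% and 13.2%; with SDs of 0.6 and 0.7 they were 15.3%, 11.5% and 11.1%.

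**5. Power when the high-dose arm starts lowest** (33% against 19%). The chi-square has 73.7-74.7% at r = 0.7 and 79.1-79.4% at 0.85, against 81.2-83.6% adjusted.

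**6. Over all trials.** Error is about 9.5-10% for the chi-square against 10-10.7% adjusted. Power is 81.8-82.7% against 81.9-82.6%. With all ten terms, adjusted error is 10.4-11.3%.

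**7. Events per term.** Expected events are 93 × (0.33 + 0.19) = 48.4. Three terms give 48.4/3 = 16.1 each. Ten terms (race/ethnicity as two) give 4.8.

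**8. The estimate changes meaning.** In a separate simulation with an assumed log odds ratio of −0.5 per SD for each score, the mean treatment log odds ratio moved from −0.80 without the scores to −0.93 with them.

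**The case against.** The strongest reply is that nothing decisive depends on this. The model is exploratory, in a phase II trial, and the open list does not exclude the baseline scores. Averaged over all randomisations, adjustment improves neither error nor power, and its Wald test runs slightly above nominal. The benefit appears only after selecting trials with unlucky baselines, which would be so for any prognostic covariate. All of this stands.

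The choice of correlation also matters. Section 13.2 plans 33% and 19%. At r = 0.7, unchanged scores already give 32-34% AIA, so 19% would need scores to improve while women start an AI. Under the main SDs, both planned rates fit best at about 0.85-0.9, where the benefit is smallest. Correlations below 0.7 fit worse still and are not used here.

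A reader might infer that the chi-square is biased, that false positives are roughly doubled, or that the trial is underpowered. The documents support none of these: the test is valid under randomisation, the sample size reproduces, and no correlation or SD is given from which a large inflation could be derived. Nor does the adjusted model hold its error exactly in every imbalance; the simulated range reaches nearly 13%.

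What survives is narrow. Descriptive tables would reveal an imbalance but would not settle in advance how to account for it.

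**Conclusion.** The point holds as a minor, optional improvement. The plan names in advance neither of the two covariates tied to its endpoint by construction, although both are collected. Pre-specifying them brings no material gain over all trials. In the 10% of null trials where the high-dose arm starts highest, it brings error of about 11-14% (r = 0.85-0.9) or 15-17% (r = 0.7) to roughly 10-13%. These figures rest on assumed correlations, SDs and baseline means. Confidence is high on what the plan says and moderate on the size of the benefit. No primary conclusion depends on it.

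**What to change.** In section 13.4:

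- Keep the chi-square as the primary test.
- Pre-specify one adjusted logistic model for week-12 AIA with treatment, baseline HAQ-II and baseline visual analog pain, both scores continuous.
- Report the model with the six listed covariates added as a further exploratory analysis. Do not let a judgement of sparseness made on the data decide which model is reported.
- Keep the section 12.1.2 rule for a missing week-12 HAQ.
- State that the adjusted odds ratio is conditional on the baseline scores and is not the same quantity as the unadjusted effect.

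The cost is a few sentences. No new data, visits or patients are needed, and alpha, sample size and the primary test do not change. The downside is two more model terms and a Wald test that runs slightly above nominal on average.

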13.5 Secondary Endpoints

Compliance will be determined via counting remaining pills in patient’s bottles at weeks 12, 24, 36, and 52 weeks. Compliance rate over 52 weeks of AI therapy will be compared between the two arms using longitudinal data analysis. The association between low baseline vitamin D levels and AIA will be assessed using the multivariate logistic regression model with adjusting for treatment effect and other confounding factors.

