2.2 Secondary Objectives

- 2.2.1 To assess whether high dose Vitamin D supplementation, as compared to standard dose, leads to improved compliance with aromatase inhibitor therapy.
- 2.2.2 To assess whether low baseline serum 25-hydroxyvitamin D levels are a risk factor for developing AIA

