12.1 Definitions

12.1.1 **Evaluable for toxicity:** All patients will be evaluable for toxicity from the time of their first treatment with Vitamin D.

12.1.2 **Evaluable for response:** All the patients who have been randomized will be considered evaluable for response, regardless of how much treatment they have received,

consistent with an intention to treat analysis. These patients will have their response classified according to the definitions stated below. Any patient who began the study medication, but does not complete the HAQ at 12 weeks, will be deemed to be a study failure (i.e. the development of AIA will be assumed), consistent with an intention to treat analysis.

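### The baseline vitamin D model in section 13.5 has no missing-data rule of its own, so on the natural reading women with no week-12 questionnaire count as arthralgia cases, which dilutes and could distort objective 2.2.2

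*Combined protocol and SAP*

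**What the plan says.** Objective 2.2.2 is "To assess whether low baseline serum 25-hydroxyvitamin D levels are a risk factor for developing AIA". The analysis is one sentence in section 13.5: "The association between low baseline vitamin D levels and AIA will be assessed using the multivariate logistic regression model". The covariates it plans are treatment and confounders that it does not name. That section gives no time point, analysis set or handling of missing questionnaires for this model.

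AIA is defined in section 12.2 as an "increase in HAQ-II score from baseline by 0.2 or greater; or 2) increase in visual analog pain score by 0.3 or greater". Section 12.1.2 adds two rules. First, "All the patients who have been randomized will be considered evaluable for response, regardless of how much treatment they have received". Second, for a woman who began study medication but has no week-12 HAQ, "the development of AIA will be assumed". Neither rule is limited to the comparison of arms.

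Section 13.4 makes week 12 the time point of the primary test and sets all tests at one-sided 0.10. Section 13.2 assumes 5% dropout in the first 12 weeks.

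**The concern.** In the randomised comparison, counting a missing form as a failure is a defensible penalty, because randomisation balances the reasons for missing a visit in expectation. Baseline 25(OH)D is not randomised. If the same coded variable is the outcome of the risk-factor model, the model estimates predictors of arthralgia or non-attendance, whereas objective 2.2.2 asks about arthralgia alone.

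There are two consequences. Dropout unrelated to vitamin D adds the same proportion of false cases to both vitamin D groups and pulls a real odds ratio towards 1. Dropout that is more common at low vitamin D, for reasons the covariates do not capture, would show up as an arthralgia risk. Objective 2.2.2 is one of only two secondary objectives, so its result is likely to be quoted in its own right.

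**Working it through.** **Inputs from the plan.** AIA 33% and 19% by arm, so 26% on average at 1:1 (13.2); one-sided 0.10 (13.2, 13.4); 186 women and 5% dropout by week 12 (13.2). The plan gives no sample size or power for objective 2.2.2. As a check on the inputs, the pooled two-proportion formula for 33% vs 19% at one-sided 0.10 and 80% power gives 87.6, so 88 per arm, and 88/0.95 = 92.6, so 93. Both numbers appear in the plan.

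**Assumptions, not in the plan.** The plan sets no cut-off for low vitamin D. I use a 93/93 split and, from the cohort cited in section 1.5 (41% + 46% = 87% below 30 ng/mL), a 162/24 split. All dropout rates by vitamin D level and all true associations below are assumed. All results are unadjusted.

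**Assumed cases at 5% dropout.**
- Coded only because the form is missing: 0.05 × 186 = 9.3 women.
- Observed cases: 0.26 × 0.95 × 186 = 45.9.
- Coded cases: 45.9 + 9.3 = 55.2, a rate of 29.7%.
- Share assumed: 9.3/55.2 = 16.8%.

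**Dilution.** With true risk p and dropout d, the coded risk is d + (1 − d)p. Take p = 35% vs 20% and d = 5% in both groups.
- True odds ratio: (0.35/0.65)/(0.20/0.80) = 2.15.
- Coded risks: 0.05 + 0.95 × 0.35 = 38.25% and 0.05 + 0.95 × 0.20 = 24.0%.
- Coded odds ratio: (0.3825/0.6175)/(0.24/0.76) = 1.96.
- Power, by exact enumeration of the one-sided pooled Z test: 79.4% with the coded outcome in 93/93; 83.7% with observed outcomes in 88/88 (93 × 0.95 = 88.35).

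A second case points the same way. With 46% low, a true odds ratio of 2.0 and 5% dropout, the rule gives 1.83 with power about 0.72; observed outcomes give 2.0 with about 0.76. At 10% dropout the rule gives 1.71.

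**Creation.** True AIA is 26% in both vitamin D groups, with exact enumeration at one-sided 0.10.

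| Dropout, low vs higher vitamin D | Coded risks | Odds ratio | False positives, 93/93 | False positives, 162/24 |
|---|---|---|---|---|
| 5% vs 5% | 29.7% / 29.7% | 1.00 | 10.0% | 10.0% |
| 6% vs 4% | 30.4% / 29.0% | 1.07 | 14.4% | 12.7% |
| 8% vs 2% | 31.9% / 27.5% | 1.24 | 26.7% | 19.9% |

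At 93/93 the last two rows average the planned 5%. At 162/24 the 8% vs 2% row averages 0.87 × 8% + 0.13 × 2% = 7.2%.

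**Observed outcomes when women with AIA leave more often.** If women with AIA drop out at rate d1 and the others at d0, the observed odds in each group are [p/(1 − p)] × (1 − d1)/(1 − d0). The second factor is the same in both vitamin D groups and cancels, so the odds ratio stays 2.15. With d1 twice d0 and 5% dropout overall (d0 = 3.9%, d1 = 7.8%), the rule gives 2.00; with d1 three times d0 it gives 2.02.

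**The case against.** **The link is not explicit.** Section 12.1.2 speaks of response, study failure and intention to treat, which is the language of an arm comparison. Section 13.4 points to 12.2 for the definition of AIA, and 13.5 cites neither. The rule covers only the week-12 HAQ in women who began study medication. A reader might infer that the plan expressly puts assumed cases into the risk-factor model; it does not. What remains is that 13.5 uses the same endpoint term and offers no other rule, so a programmer following the plan would carry the coded variable across.

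**The planned covariates may remove the false signal.** The figures above are unadjusted. Suppose 8% vs 2% dropout arises wholly from one binary factor present in 80% of the low group and 20% of the others. Dropout is then 10% with the factor and 0% without it (0.8 × 10% = 8%; 0.2 × 10% = 2%), and within each level of the factor the odds ratio is 1.00. A simulation of this case gave 26% false positives unadjusted and 9.7% with the factor in the model. This stands: inflation needs dropout that differs by vitamin D after adjustment, and nothing in the documents shows that it will. Adjustment does not cure the dilution, and 13.5 does not list its confounders.

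**Observed-only analysis also rests on an assumption.** Section 1.2 cites a pilot in which 13% stopped AI therapy because of arthralgia, so some missing women may be true cases. The cancellation above answers this as long as AIA changes dropout by the same factor in both vitamin D groups. If it does not, the sensitivity analyses are needed.

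**The adjusted model in 13.4.** Section 13.4 says "development of AIA will be assessed using logistic regression, adjusting for potential confounders", and a reader might infer that this model has the same fault. It sits directly after the arm test and is naturally read as its covariate-adjusted version, where the rule is defensible. The point does not extend to it.

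**Conclusion.** The point holds for the baseline vitamin D model in section 13.5 and should be corrected there. On the natural reading, about one coded case in six at the planned dropout is a missing form.

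The dilution needs no differential dropout, but it is moderate: an odds ratio of 2.15 becomes 1.96, and power is about 79% where observed outcomes would give about 84%, for an assumed 35% vs 20% and a 93/93 split. The false association is conditional. At 6% vs 4% dropout the false-positive rate is 13–14%, and at 8% vs 2% it is 20–27%, depending on the share with low vitamin D. Those dropout rates are assumptions and the results are unadjusted.

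A reader might infer that a positive finding for objective 2.2.2 would be an artefact of dropout. The documents do not support that: they give no evidence that dropout varies with baseline vitamin D, and equal dropout leaves a null association at 1.00. The primary result is not affected.

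**What to change.** Change section 13.5 only, to read along these lines: *The baseline 25(OH)D model uses observed week-12 AIA (women with a completed week-12 HAQ-II), adjusted for treatment and the covariates listed in 13.4; multiple imputation and the missing-equals-AIA coding are sensitivity analyses.*

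Leave the primary comparison, the interim look and the 13.4 adjusted arm model on the all-randomised set. The change should be made before the outcome data are analysed.

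The cost is wording, plus about 5% fewer women (about 177 rather than 186) in this one secondary model. In the equal-dropout scenarios above, that loss is more than offset by removing the dilution. Sample size and patient procedures do not change.
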